Cycle 6+/- Follow up visits will occur every 14 days (+/- 2 days) for all subjects who remain on trial:

- Physical Exam
- Weight

- Vital Signs (pre-infusion)
- ECOG Evaluation
- Hematology panel: CBC with differential, platelets (pre-infusion)
- Chemistry panel and serum pregnancy (pre-infusion same tube). Serum pregnancy to be completed every 2 cycles.
- Urinalysis (pre-infusion)
- CRP (pre-infusion)
- PK Sampling (pre-infusion)
- Study Drug infusion
- Vital signs (60 minutes post-infusion)
- PK Sampling (30-90 minutes post-infusion)
- Adverse Event monitoring
- Concomitant Medications
- Tumor Measurements (every 8 weeks, i.e. within 7 days prior to C9D1, C13D1 etc.). Upon documentation of radiographic progression, confirmatory tumor measurements to be repeated at 4 weeks +/- 3 days only for patients who elect to continue on therapy until confirmation of progression. If this scan confirms progression, treatment is to be discontinued. If the confirmatory measurements indicate stable disease or better, the patient may elect to continue treatment with radiographic tumor assessments every 8 weeks from Day 1 of the current treatment cycle until progression.

End of Study Visit- This visit should be completed within 14 days for any subject who elects to come off trial or who comes off due to AEs, toxicities, or decline in performance status:

- Physical Exam
- Weight
- Vital Signs
- ECOG Evaluation
- Hematology panel: CBC with differential, platelets
- Chemistry panel
- Urinalysis
- CRP
- Adverse Event monitoring
- Serum Pregnancy
- PK Sampling
- EORTC QLQ-C30
- Concomitant Medications / Non-Drug Therapies review
- DEXA Scan--for any subject who completes visits at least through C3D1, but discontinues prior to C5D1
- Tumor Measurements--for subjects with clinical progression, every effort should be made to obtain radiographic restaging. If subjects are discontinued due to evidence of progressive disease, then tumor measurements do not need to be repeated.

Follow up for Overall Survival

Subjects, who come off trial for any reason after C1D1, will be contacted by phone after 30 days of the last dosing visit for adverse events and ECOG performance status, and at every 4-6 weeks

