5.4 STUDY CALENDAR

Study Procedures	Screening	Cycles 1-4	Cycle 5	Cycle 6+	End of Study Visit	Follow-Up for Survival
	Day -14 (C1D1) must occur within 7 days of randomization:	Day 1 (+/- 2 days)	Day 1 (+/- 2 days)	Day 1 (+/- 2 days)	Within 14 days of treatment discontinuation	Every 4-6 Weeks
Study Drug Infusion		X	X	X		
Informed Consent	X					
Medical History	X					
Serum Pregnancy Test ^d	X	X ^d	X ^d	X ^d	X	
Physical Exam	X	X	X	X	X	
Height	X					
Weight	X	X	X	X	X	
Vital Signs ^a	X	X ^a	X ^a	X ^a	X	
ECOG Evaluation	X	X	X	X	X	X
Hematology Panel: CBC with differential, platelets	X	X	X	X	X	
Chemistry Panel ^b	X ^b	X ^b	X ^b	X ^b	X ^b	
PT/aPTT/INR	X					
Urinalysis ^c	X ^c	X ^c	X ^c	X ^c	X ^c	
PK Sampling ^e		X ^e	X ^e	X ^e	X ^e	
CRP ^f	X ^f	X ^f	X ^f	X ^f	X ^f	

DEXA Scan ^g	X ^g		X ^g		Only Patients that discontinue between C3D1 and C5D1	
EORTC-QLQ-C30 ^h	X		X			
Tumor Measurements ^{i, j, k}	X ⁱ		X ⁱ After DEXA scan	X ^{i, j} Every 8 Weeks	X ^{i, k} Unless discontinued for Progressive Disease	
Adverse Events	X					
Concomitant Medications	X					

Footnotes for Study Calendar:

^a Blood pressure, pulse and temperature. Pre and 60 minutes post infusion.

^b Sodium, potassium, chloride, bicarbonate, BUN, creatinine, glucose, calcium, magnesium, albumin, alkaline phosphatase, total bilirubin, SGOT [AST], and SGPT [ALT] will be analyzed locally as standard of care for safety prior to infusion. A second pre-infusion sample must be obtained and shipped to the central lab.

^c Bilirubin, glucose, ketones, leukocytes, nitrites, blood, pH, specific gravity, protein and urobilinogen will be analyzed will be analyzed locally as standard of care for safety prior to infusion. A second pre-infusion sample must be obtained and shipped to the central lab.

^d Pregnancy Test Every 2 Cycles. Sample sent to the central lab for chemistry will be used for analysis, no additional blood draw required. Results will be sent from central lab to the site

^e Pre and post-infusion PK samples to be collected. One 6 ml Na-Heparin tube will be used to collect blood from subjects at each PK sampling time point. Note: during visits when subjects are receiving MABp1, the "post-infusion" sample will be collected between 30-90 minutes post-infusion.

^f CRP will be assayed from the Chemistry sample on Screening, Cycles 1-5, Cycles 6+, End of Study/Early Termination and Unscheduled Visits.

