- Overall survival (OS) will be the primary endpoint of this study, survival time will be defined as the duration from the date of randomization until death. Subjects who are alive at the data inclusion cutoff date for the analysis will be censored at that date and survival time will be defined as time from randomization to censor date. Patients lost to follow-up and untraceable for survival status will be censored on the last date subject was known to be alive or lost to follow-up. The overall survival between the Xilonix™ + BSC group and placebo + BSC group will be compared using an unadjusted log-rank test.

3.2 Secondary Efficacy Endpoints:

Secondary efficacy variables will include 1) change in lean body mass (LBM) measured by dual-energy X-ray absorptiometry (DEXA) scans, 2) change in function, symptoms and overall quality of life assessed through the cancer-specific EORTC QLQ-C30¹ questionnaire, 3) change of platelet counts, 4) progression free survival (PFS), 5) objective response rate (ORR) 6) disease control rate (DCR)

The change from baseline on LBM, EORTC score, and platelet count will be calculated by subtracting the baseline (screening) value from that at follow-up (cycle 5 day 1 or off-study visit for patients who completed at least cycle 3 day 1).

Quality of life (QoL) in patients participating in the trial will be evaluated using the European Organization for Research and Treatment of Cancer (EORTC) version 3.0 questionnaire (Appendix). The EORTC QLQ-C30 questionnaire incorporates nine multi-item scales: five functional scales (Physical, Role, Cognitive, Emotional and Social); three symptom scales (Fatigue, Pain and Appetite loss); and a Global Health Status/QoL scale. Each item, excepting Global Health Status, is answered on a four-point scale: “not at all”, “a little”, “quite a bit”, and “very much”. Response to Global Health Status is measured on a 1 to 7 scale, 1 being “very poor” and 7 being “excellent”. Using EORTC specified methodology (Appendix); responses to all the scales will be linearly transformed to reach the scale range 0 to 100.

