7.1 Analysis Populations:

The primary efficacy analysis will be conducted on an intent-to-treat (ITT) basis. The ITT population will consist of all randomized patients. Patients will be grouped according to treatment group.

Some major changes were made to protocols version V3.0 onwards. Prior to V3.0 this trial was an open label, 1:1 random allocation study where patients received MABp1 (3.75 mg/kg) plus BSC or megestrol acetate plus BSC. Some of the major changes to protocols V3.0 onwards were a double blind placebo controlled design with 2:1 allocation ratio. Dosing regimen also changed from 3.75 mg/kg to 7.5 mg/kg of MABp1. Given the nature of change to the study design patients enrolled on protocols prior to V3.0 modification will not be included in the analysis.

A secondary analysis of the efficacy endpoints will be performed on Per Protocol (PP) patients. The PP population will be defined as those patients in the ITT set who are compliant with the study protocol. Patients will be grouped according to treatment groups.

The Safety analysis will be based on the Safety Population, defined as enrolled patients receiving at least one dose of study drug. Patients will be grouped according to actual treatment received.

7.2 Incomplete Follow-up:

Patients discontinued or lost prior to cycle 3 visit (and therefore not having the second DEXA), or those discontinuing between cycles 3 and 5 but did not complete off-study visit, will not be included for secondary efficacy outcome assessment for absolute change in LBM, or EORTC endpoints.

For the PFS assessment, patients discontinued or lost without evidence of tumor progression will be censored according to Table 1 .

7.3 Missing Data:

Every effort will be made to identify and recover the missing data from the centers. If the data remained missing following such efforts, and contributes 2% or more of total number of patients for the continuous co-variables selected for the Cox model, it will be imputed through multiple imputations (using SAS PROC MI, pooled by PROC MIANALYZE option). Sensitivity analysis will be performed to assess the effect of imputation.

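### The study calendar omits the End of Study EORTC QLQ-C30 that the visit list requires and SAP 3.2 uses, and SAP 7.2 excludes pre-cycle 3 leavers from EORTC change with a DEXA remark relevant only to lean body mass

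*SAP*

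**What the plan says.** **Collection.** In protocol 5.4 (Study Procedures), the End of Study visit is set out as follows: "This visit should be completed within 14 days for any subject who elects to come off trial". The sentence goes on to subjects who come off for adverse events, toxicity or declining performance status. The EORTC QLQ-C30 is on that visit's list without a condition. The DEXA on the same list carries one: "DEXA Scan--for any subject who completes visits at least through C3D1, but discontinues prior to C5D1".

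In protocol 5.4 (Study Calendar), the row "EORTC-QLQ-C30 ^h" has a mark at Screening and at Cycle 5 and nothing under End of Study. In the DEXA row the End of Study cell is filled: "Only Patients that discontinue between C3D1 and C5D1". The calendar's DEXA footnote covers the off-study scan. The EORTC footnote describes the instrument and gives no timing.

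**Analysis.** SAP 3.2 defines the follow-up value for change in LBM, EORTC score and platelets as "cycle 5 day 1 or off-study visit for patients who completed at least cycle 3 day 1". SAP 7.5 gives the follow-up as week 8 or the end of study visit, names the EORTC score as an example, and states no cycle 3 condition. SAP 7.2 excludes from absolute change in LBM, or EORTC endpoints, those it describes as "Patients discontinued or lost prior to cycle 3 visit (and therefore not having the second DEXA" (closing bracket omitted here), together with those who stop between cycles 3 and 5 without an off-study visit. SAP 7.3 imputes no secondary outcome except platelets. SAP 8.4.2 (Secondary Effectiveness Endpoints) counts patients with no follow-up assessment as EORTC non-responders and as clinical non-responders.

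**The concern.** Quality-of-life change is a named secondary endpoint with one scheduled on-treatment questionnaire, at C5D1. For a living patient who stops before then, the End of Study form is the only follow-up score. Two separate gaps touch it, in different patients.

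The first concerns collection and affects patients who leave between C3D1 and C5D1. The SAP plans to use their off-study score, but the calendar does not ask for it. A site following the calendar would do the off-study DEXA and skip the questionnaire. A questionnaire not given at the time cannot be recovered later.

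The second concerns analysis and affects patients who leave before C3D1. The visit list collects their questionnaire, and SAP 7.2 then keeps it out of absolute change. The only remark it attaches is about a scan that has no bearing on the EORTC. The absolute-change comparison then describes only patients who stayed at least to C3D1.

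**Working it through.** The plan states no figure on this point, so there is none to reproduce. The check is a comparison of the texts by time of leaving.

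| Patient stops | EORTC at End of Study: visit list | EORTC at End of Study: calendar | EORTC change analysis | Responder analyses |
|---|---|---|---|---|
| Before C3D1 | Required | Blank | Excluded (SAP 3.2, 7.2) | EORTC non-responder under the 3.2 follow-up definition; clinical non-responder in any case, as there is no second DEXA |
| From C3D1, before C5D1 | Required | Blank | Off-study score used if it exists (SAP 3.2); otherwise out, with no imputation (SAP 7.3) | Scored from the form if it exists; otherwise EORTC and clinical non-responder, even with a measured LBM gain |
| After the C5D1 assessments | Required | Blank | C5D1 score used | C5D1 score used |

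The calendar gap costs outcome data in the second row. SAP 7.2 acts on the first row.

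**Wording of SAP 7.2.** If its reference to EORTC endpoints means absolute change only, it is compatible with the non-responder rule in 8.4.2. If it means all EORTC endpoints, the two contradict each other. It is also unsettled whether an early leaver's End of Study form counts as a follow-up assessment: SAP 3.2 implies not, while 7.5 could be read as saying it does.

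**Scale of the calendar gap.** The number who leave alive between C3D1 and C5D1 is not given. Each 1% of 600 patients is 6 forms (4 of 400 and 2 of 200 if shares are equal). If a share *s* of an arm loses its form and a fraction *r* of those would have met the EORTC criterion, the arm's responder rate falls by *s* × *r*. That is at most 1 percentage point for each 1% lost.

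**Scale of the SAP 7.2 exclusion.** The number who leave alive before cycle 3 is not given either. Assume 5% to 20% per arm, worsening 10 to 20 points more than the rest:
- patients excluded: 0.05 × 600 = 30, to 0.20 × 600 = 120
- shift in an arm's mean change = share excluded × extra worsening: 0.05 × 10 = 0.5, to 0.20 × 20 = 4 points too favourable
- between-arm bias: 0 if the shares and the extra worsening are equal; if the shares differ by 5 percentage points, 0.05 × 10 = 0.5, to 0.05 × 20 = 1 point

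These ranges come from the assumptions, not from trial data.

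**The case against.** **The cycle 3 limit may be a minimum-follow-up rule.** SAP 3.2 applies the same C3D1 minimum to platelets, which need no scan and are measured at every cycle. SAP 7.2 also words the missing DEXA as a consequence of leaving early. A reader might infer that questionnaires are discarded because another test was not done. The documents do not establish that. What remains is that 7.2 covers two endpoints in one sentence, gives only an LBM-specific remark, and leaves its scope over the EORTC open.

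**Very early scores change what is estimated.** Protocol 10.4 sets the change at 8 weeks. A score from a patient who left before C3D1 (day 28 of treatment) measures something different, and statisticians could reasonably disagree about pooling it. This stands, and it is why these scores belong in a sensitivity analysis and not in the main one.

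**The visit list is the detailed instruction, and the calendar may be misread.** A site may well follow the list. The calendar was read from extracted text, in which the adverse event and concomitant medication rows show a single mark although the visit lists require both at every treatment visit. Some spanning cells were therefore probably lost. The DEXA entry in the End of Study column did come through, which suggests that the column is intact, but the original page has to be checked.

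**Early deaths do not measure the loss.** The SAP hazards give deaths by day 28 (28/30.4375 = 0.92 months) of 1 − exp(−0.116 × 0.92) = 10.1% on MABp1 and 1 − exp(−0.151 × 0.92) = 13.0% on placebo. It is tempting to read these as the size of the problem. Patients who have died complete no questionnaire, and inclusion criterion 12, which asks for fitness to stay three months, may make early deaths fewer.

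**Conclusion.** Subject to confirming the calendar cell, the visit list and the calendar conflict on a value that SAP 3.2 needs. This is the firmer of the two parts, because a missed form cannot be recovered or imputed and turns the patient into a non-responder whatever they would have reported. The SAP 7.2 part holds as a matter of clarity and of a missing sensitivity analysis. A minimum-follow-up rule for the main analysis is defensible, but the text does not give that reason and does not say how far the rule reaches.

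A reader might go further and say that quality of life is lost in the patients who decline first. The documents do not support that. Measured scores are missing from absolute change, but the responder analysis retains these patients as non-responders. Nor would any change to the EORTC rule make pre-C3D1 leavers eligible as clinical responders, since that also needs a second DEXA.

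The size is unknown because the documents give no discontinuation rates. Under the assumed 5% to 20%, the SAP 7.2 exclusion moves each arm's mean by 0.5 to 4 points, and the between-arm difference by about 0 to 1 point if the shares differ by no more than 5 percentage points. This is a secondary endpoint; the primary analysis of overall survival is not affected. The change should be made, and its weight is moderate.

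**What to change.** - **Calendar.** After confirming the cell on the original page, mark the EORTC QLQ-C30 in the End of Study column to match the visit list, at least for subjects who discontinue before the C5D1 questionnaire.
- **SAP 7.2.** State the LBM and EORTC rules in separate sentences and attach the DEXA remark to LBM only. Say whether the EORTC exclusion covers absolute change alone, and give the reason for any minimum follow-up.
- **Alignment.** Make 7.2 agree with 3.2, 7.5 and the non-responder rule in 8.4.2, including whether an End of Study form completed before C3D1 counts as a follow-up assessment.
- **Sensitivity analysis.** Keep the planned EORTC change analysis and add one that includes End of Study scores from patients who leave before C3D1.

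The cost is one calendar cell, a few SAP sentences and one extra analysis. No visit or procedure is added beyond the existing visit list. The downside is that follow-up times in the sensitivity analysis are more varied, which should be stated when it is reported.

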1.7 CORRELATIVE ANALYSIS

Analysis of serum cytokine levels has shown a reduction in IL-6 levels after treatment with Xilonix™. Of the 52 subjects, 43 had data available from screening and at week 8. One subject with Castleman’s disease, however, was not included in the analysis as their serum levels were 150 times greater than the cohort average. The mean serum IL-6 levels for these 42 subjects was 20.8±23.4 (median 12.8) pg/ml, which decreased to a mean of 15.9±27.1 (median 7.6; p=0.08) after 8 weeks of treatment. This decrease was even more pronounced when stratified by LBM response. IL-6 levels for subjects who increased LBM (N=20) changed from an average of 16.5±12.5 (median of 12.3) to an average of 10.9±12.9 (median of 6.2 pg/ml; p=0.044). Those

[figure not shown]
subjects who did not respond had non-statistically significant increases in IL-6 levels. Figure 1.9 details these responses.

Figure 1.9

Plasma IL-6 levels were measured by ELISA. Overall for the entire patient population, plasma IL-6 levels declined. However, stratification of the data among patients that had increases in LBM versus those that lost LBM revealed differences. LBM increase was associated with declining serum IL-6 at week 8, while patients with LBM loss did not show reduction in plasma IL-6 levels (Overall population (n=43): Average change -4.9 ± 26 (median -2.7) pg/ml, $p=0.08$; Responders (n=20): Average change -5.6 ± 13 (median -3.2) pg/ml, $p=0.044$; Non-responders (n=6): Average change -3.8 ± 21 (median -0.4) pg/ml, $p=0.91$).

IL-1 α is expressed on the surface of platelets, thus platelet numbers were analyzed across dose cohorts. Increases in platelet counts are known to occur in many advanced cancer patients, and can be a prognosticator of disease progression³⁰. In this trial, platelet counts appeared to increase over time (Figure 1.10), however, there also appeared to be dose dependent abrogation of platelet compartment expansion. This is the likely result of decreasing serum IL-6 levels, as there was no evidence of platelet destruction in these patients.

Figure 1.10

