Platelet counts were determined as part of routine blood analysis. Platelet numbers showed a trend of increasing over time in advanced cancer patients and can be a prognosticator disease progression. Platelet counts presented are differences between those measured prior to treatment and at week 8 (after three rounds) of antibody therapy. The 3.75mg/kg dose cohort was initially provided every three weeks. This dosing was increased in frequency to every two weeks (2 week).

Flow cytometry was also used to examine IL-1 α expression on CD14+CD16+ monocytes. Treatment with Xilonix™ resulted in a trend of reducing IL-1 α +CD14+CD16+ monocytes (as a percentage of CD14+CD16+). This reduction was observed without an overall decrease in the absolute number of monocytes, which suggests Xilonix™ binding to IL-1 α on the surface of these potentially pathogenic cells. Decreases in IL-1 α +CD14+CD16+ monocytes appeared to rebound towards the end of dosing cycles (Figure 1.11).

Figure 1.11

[figure not shown]

[figure not shown]
Chart shows IL-1 α expressing monocytes present in peripheral blood as percentage of CD14+CD16+ monocytes. Blood samples were analyzed from patients at screening, prior to infusion with Xilonix™, until cycle 5, day one post infusion (C2D15). The n values change over time, as patients are lost from study. Trend appears to show treatment reduction in exposed IL-1 α present on this monocyte subset.

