*Urinalysis, Hematology and Chemistry panels that are obtained for the purpose of screening a subject, and that are drawn within 72 hours of C1D1, may also be used for the C1D1 baseline safety lab values.

- Urinalysis (pre-infusion)
- CRP (pre-infusion)
- PK Sampling (pre-infusion)
- Study Drug infusion
- Vital signs (60 minutes post-infusion)
- PK Sampling (30-90 minutes post-infusion)
- Adverse Event monitoring
- Concomitant Medications

Cycle 2 Day 1 +/- 2 days (C2D1):

- Physical Exam
- Weight
- Vital Signs (pre-infusion)
- ECOG Evaluation
- Hematology panel: CBC with differential, platelets (pre-infusion)
- Chemistry panel and serum pregnancy (pre-infusion same tube)
- Urinalysis (pre-infusion)
- CRP (pre-infusion)
- PK Sampling (pre-infusion)
- Study Drug infusion
- Vital signs (60 minutes post-infusion)
- PK Sampling (30-90 minutes post-infusion)
- Adverse Event monitoring
- Concomitant Medications

Cycle 3 Day 1 +/- 2 days (C3D1):

- Physical Exam
- Weight
- Vital Signs (pre-infusion)
- ECOG Evaluation
- Hematology panel: CBC with differential, platelets (pre-infusion)
- Chemistry panel (pre-infusion)
- Urinalysis (pre-infusion)
- CRP (pre-infusion)
- PK Sampling (pre-infusion)

- Study Drug infusion
- Vital signs (60 minutes post-infusion)
- PK Sampling (30-90 minutes post-infusion)
- Adverse Event monitoring
- Concomitant Medications

Cycle 4 Day 1 +/- 2 days (C4D1):

- Physical Exam
- Weight
- Vital Signs (pre-infusion)
- ECOG Evaluation
- Hematology panel: CBC with differential, platelets (pre-infusion)
- Chemistry panel and serum pregnancy (pre-infusion same tube)
- Urinalysis (pre-infusion)
- CRP (pre-infusion)
- PK Sampling (pre-infusion)
- Study Drug infusion
- Vital signs (60 minutes post-infusion)
- PK Sampling (30-90 minutes post-infusion)
- Adverse Event monitoring
- Concomitant Medications

Cycle 5 Day 1 +/- 2 days (C5D1):

- Physical Exam
- Weight
- Vital Signs (pre-infusion)
- ECOG Evaluation
- Hematology panel: CBC with differential, platelets (pre-infusion)
- Chemistry panel (pre-infusion)
- Urinalysis (pre-infusion)
- CRP (pre-infusion)
- PK Sampling (pre-infusion)
- Study Drug infusion
- Vital signs (60 minutes post-infusion)
- PK Sampling (30-90 minutes post-infusion)
- Adverse Event monitoring
- Concomitant Medications
- EORTC QLQ-C30
- DEXA scan for lean body mass/body composition (+/- 3 days of C5D1)
- Tumor Measurements (+/- 3 days of C5D1- **AFTER DEXA SCAN**)

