The primary efficacy analysis will be performed using the available data, no imputation will be made. Also the missing data for primary or secondary outcome variables, except for platelet counts, will not be imputed. For platelet counts missing on cycle 5 visit, the available value on cycle 3 or cycle 4 visit will be carried forward. Imputation of missing data will not be carried out for descriptive analyses.

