EORTC: Longitudinal and descriptive analysis will be performed to assess patient reported outcomes (PRO). The EORTC survey results will be converted to domain specific scores using the prescribed algorithm (Appendix A). Scores on the EORTC QLQ-C30 functional and symptom scales will be summarized according to the randomization groups. The EORTC survey responses will be converted to domain specific scores using the prescribed algorithm. Scores on EORTC QLQ-C30 functional and symptom scales will be summarized according to the randomization groups. Descriptive statistics of PRO score will be summarized by treatment group.

Patients showing stabilization or improvement from baseline (≤ 0 change) on any two of the three symptom scales (pain, fatigue, appetite loss) will be considered EORTC responders. Patients experiencing reduction or worsening on the symptom scales will be defined as non-responders. Patients missing the follow-up assessment will be considered non-responders. The comparison of responder rate and absolute change will be performed similar to as described for LBM.

Clinical Response Rate: Patients responding on LBM (≥ 0 kg change from baseline) and EORTC (≤ 0 change on any two three symptoms) will be considered Clinical Responders. Patients missing follow-up status will be considered non-responders. Clinical Response Rate will be compared using a Pearson chi-square test. Proportion by treatment groups and relative risk estimates will be presented with CMH 95% confidence intervals.

Platelet Count: Change in platelet count from baseline to follow-up will be compared between treatment groups using the ANCOVA method described above. The last visit cycle where at least 20 patients per group are on study will be used for follow-up data cut-off for this measure. Trend line plots displaying the median platelet count over time (visit cycles) by treatment groups will be generated.

Progression Free Survival (PFS): PFS will be compared by Kaplan-Meier method using log-rank test. Kaplan-Meier plots by treatment arm will be produced, and point estimates and 95% CIs will be summarized.

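### Carrying a cycle 3 or 4 platelet count forward to a missing cycle 5 freezes a count expected to rise, with a bias set by dropout and slope in each arm, and the rule conflicts with SAP 3.2 and 8.4.2.

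*SAP*

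**What the plan says.** Platelets are the one outcome for which the SAP fills missing data. SAP 7.3 says: "Also the missing data for primary or secondary outcome variables, except for platelet counts, will not be imputed". It then gives the rule: "For platelet counts missing on cycle 5 visit, the available value on cycle 3 or cycle 4 visit will be carried forward".

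SAP 8.4.2 (Secondary Effectiveness Endpoints, Platelet Count) names the test: "Change in platelet count from baseline to follow-up will be compared between treatment groups using the ANCOVA method described above". That method is an ANCOVA on a single change score with the baseline value as covariate, judged at two-sided 0.05.

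Two other SAP rules define the follow-up value differently:

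- SAP 3.2 takes C5D1, or the off-study visit for patients who completed at least C3D1. SAP 7.5 likewise allows week 8 or the end-of-study visit.
- SAP 8.4.2 sets the platelet cut-off at the last cycle with at least 20 patients per group still on study. Protocol 10.4 has the same rule.

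Protocol 1.7, describing the earlier trial, says that "platelet counts appeared to increase over time" and that "there also appeared to be dose dependent abrogation of platelet compartment expansion". The basis is limited: "Platelet counts presented are differences between those measured prior to treatment and at week 8 (after three rounds) of antibody therapy".

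Under Protocol 5.4, platelets are drawn before every infusion and again at the End of Study visit.

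**The concern.** Carry-forward assumes that a count stays flat after the last value seen. The endpoint exists because the sponsor expects the opposite: counts rise, and the drug restrains the rise. Freezing a patient at cycle 3 or 4 removes up to two of the four intervals over which the arms are expected to separate. The ANCOVA then treats the filled value as measured. A patient whose only post-baseline count is at cycle 2 cannot be filled at all.

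No sensitivity analysis covers this. The one in SAP 7.3 follows the multiple imputation of Cox covariates, and the one in SAP 7.4 concerns extreme values.

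At stake are the estimate and test for one named secondary endpoint. Because three rules point to different follow-up values, there is also room to choose among them after the data are seen.

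**Working it through.** **No figure to reproduce.** The documents give no platelet sample size, power, SD, slope or dropout. The slopes and filled shares below are assumptions, except where deaths are derived from the SAP hazards.

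**Formula.** Let r be the rise per two-week cycle in an arm and d the share of cycle-5 values that are filled, half from cycle 3 (two cycles carried) and half from cycle 4 (one cycle carried). The mean carried is 1.5 cycles. Counting from C1D1 and assuming a linear rise, the true change at C5D1 is 4r, and

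understatement in the arm = d x 1.5 x r.

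**Illustration.** Assume r = 10 (placebo) and 5 (drug), in 10^9/L per cycle. The true difference is 4 x 10 - 4 x 5 = 20.

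| Filled, placebo / drug | Placebo understated by | Drug understated by | Difference obtained |
|---|---|---|---|
| 25% / 25% | 3.75 | 1.875 | 18.1 (-9%) |
| 20% / 30% | 3.0 | 2.25 | 19.25 (-4%) |
| 30% / 20% | 4.5 | 1.5 | 17.0 (-15%) |

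The difference is inflated only when 7.5 x d(drug) exceeds 15 x d(placebo), that is, when the drug arm's filled share is more than twice placebo's.

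**Equal slopes.** With r = 10 in both arms there is no true difference. Filling 30% / 20% gives -1.5, 20% / 30% gives +1.5, and equal shares give 0. Only with equal slopes does dropout alone set the sign.

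**Deaths alone.** SAP section 5 assumes medians of 4.6 and 6.0 months. One cycle is 14/30.4375 = 0.46 months. Among patients alive at C3:

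- Placebo: 6.70% die between C3 and C4 and 6.25% between C4 and C5, 12.9% in all. Share times cycles carried = 2 x 0.0670 + 0.0625 = 0.196.
- Drug: 5.17% and 4.91%, 10.1% in all. Share times cycles carried = 2 x 0.0517 + 0.0491 = 0.153.

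With slopes of 10 and 5, the understatement is 1.96 and 0.76. The difference falls by 1.2 of 20, or 6%. With equal slopes of 5, 10 or 20, the net distortion is only 0.2, 0.4 or 0.9.

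**Which visit is analysed.** With 200 placebo patients and exponential time on study (assumed), 20 remain at median x ln(10)/ln(2). C5D1 is day 56, or 1.84 months, so the 20-per-group cut-off reaches cycle 5 if median time on study is about 0.55 months or more. At assumed medians of 1, 2 and 3 months, it falls at cycle 8, 15 and 22. The visit filled under SAP 7.3 would then not be the visit analysed under SAP 8.4.2.

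**The case against.** The strongest reply is that few values may need filling. Under SAP 3.2 and 7.5, a patient who leaves between C3 and C5 contributes an off-study count, and Protocol 5.4 draws platelets at that visit, due within 14 days. Carry-forward would then be residual, mainly for deaths and missed off-study visits, and filled shares of 20 to 30% may be much too high. This stands as a limit on the size. It does not settle the rule, because the SAP never says that the off-study value takes precedence over carry-forward.

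The evidence of a rise is also thin. It is a pre-treatment versus week 8 comparison in an earlier advanced-cancer trial with doses up to 3.75 mg/kg, worded cautiously, and it gives no separate cycle 3 to cycle 5 change. A linear rise is therefore an assumption. The SAP does plan median trend plots by cycle and does not impute for descriptive analyses, so the observed course will be visible, although it will not be the tested comparison.

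The proposed model is not assumption-free either. It treats data as missing at random, which is doubtful when dropout follows deterioration, and it implies C5 values for patients who died before C5.

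A reader might infer that the arm with more dropout is the one understated, or that reversing the dropout reverses the bias. Neither follows in general. At slopes of 10 and 5 with 20% placebo and 30% drug filled, placebo has less dropout yet is understated more (3.0 against 2.25), and the difference still shrinks.

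**Conclusion.** The point holds in a limited form. Carry-forward is a poor match for a count that the sponsor expects to rise at different rates by arm, and the data for a better analysis are already collected. If the drug restrains the rise, the usual direction is towards a smaller treatment difference, even at equal dropout.

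The size cannot be fixed from the documents. At assumed slopes of 10 and 5, deaths alone give about 6%, and 25% filled in both arms gives about 9%. A reader might take the 15% in the table as the expected bias. The documents do not support that, because it rests on assumed slopes and filled shares and makes no use of off-study counts. The effect of treating filled values as measured on the standard error was not computed.

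The conflict among SAP 3.2, 7.3 and 8.4.2 rests on no assumption about slope or dropout and needs resolving in any case. The matter concerns one secondary endpoint. The primary survival analysis uses no imputation and is untouched.

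**What to change.** Replace the carry-forward rule in SAP 7.3 and the single-change platelet ANCOVA in SAP 8.4.2 with a mixed model for repeated measures on all observed counts from C2D1 to C5D1. Include treatment, visit, treatment-by-visit and baseline count, with an unstructured covariance matrix. The tested contrast is drug versus placebo at C5D1.

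In the same edit:

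- State that C5D1 replaces the 20-per-group cut-off for the test. That cut-off can still govern how far the trend plots run.
- Amend SAP 3.2 and 7.5 to say how off-study counts are assigned to visits, for example to the nearest scheduled cycle.
- Keep carry-forward, if wanted, only as a labelled sensitivity analysis.
- Say openly that the model assumes missing at random and implies C5 values for patients who died earlier, and report the number of deaths before C5 by arm.

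The cost is a short SAP amendment, a matching line in Protocol 10.4 and standard mixed-model code. No new data or visits are needed.
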